1.0 Research Introduction

1.1 Purpose/Specific Aims

This study (R33), which is being funded by the National Center for Complementary and Integrative Health (NCCIH), aims to evaluate the impact of a novel intervention, Mindfulness Oriented Recovery Enhancement (MORE), on opioid use and chronic pain among individuals receiving methadone maintenance treatment (MMT). The main goal of this study is conduct a clinical trial to assess online MORE, delivered remotely, through secure video or phone conferencing, with respect to a range of clinical outcomes. This study will involve a 2-arm individually randomized controlled trial design that compares MORE and treatment as usual (TAU).

A. Objectives

- Aim 1. Determine MORE's efficacy for increasing opioid abstinence relative to TAU.
- Aim 2. Determine MORE's efficacy for impacting secondary outcomes relative to TAU.
- Aim 3. Evaluate the degree to which MORE's impact on opioid use and pain are mediated by changes in the three core therapeutic mechanisms of MORE.
- Aim 4. Identify moderators of treatment response.

B. Hypotheses / Research Question(s)

As compared to the TAU group, the MORE group will 1) have a longer time until opioid relapse (primary outcome) and 2) have greater opioid abstinence, less other drug use, greater MMT adherence, and greater reductions in craving, pain symptoms, and emotional distress (secondary outcomes).

We hypothesize that the impact of MORE on opioid use and pain outcomes will be mediated by improvements in metacognitive awareness (mindfulness), negative emotion regulation (reappraisal), and amplification of natural reward processing (savoring).

Based on prior studies, we hypothesize that gender will moderate treatment response. ¹⁹⁻²¹ We will also explore other potential moderators like race, income, mental health, trauma, and MMT phase (i.e., stabilization/early recovery vs. maintenance/sustained abstinence).

1.2 Research Significance (Briefly describe the following in 500 words or less):

Despite the proven effectiveness of medication-assisted treatment (MAT) on opioid-use disorder (OUD), approximately 50% of people who begin MMT discontinue within 12 months, and 50% of people retained in MMT have an opioid relapse within six months. Research suggests that chronic physical pain, affecting 55%-61% of people receiving MMT, could be contributing to opioid relapse and MMT dropout. Unfortunately, effective pain management in MMT patients is challenging, as practitioners are reluctant to prescribe opioid pain medications to those with a history of substance use disorder. Therefore, alternative interventions are critical to help people in treatment for OUD to cope with their pain and improve their quality of life.

3

Version Number: 15, 2/2/2022 Protocol Number: Pro20190016877

PI Name: [name]

Protocol Title: Mindfulness Oriented Recovery Enhancement (MORE) as an Adjunct to Methadone Treatment RESERVED FOR IRB STAMP
DO NOT MODIFY THIS SPACE

Mindfulness Oriented Recovery Enhancement (MORE) is a novel intervention that addresses drug use and chronic pain, and is unique among current OUD interventions in that it helps break negative reinforcement cycles by modifying the associative learning mechanisms that process drug and non-drug related cues. ^{5,6} As a result, MORE promotes biobehavioral changes that strengthen responses to natural rewards while reducing responses to drug rewards, making the intervention more effective in helping people in MMT manage their pain and maintain long-term drug abstinence. ^{5,6} MORE, which integrates training in mindfulness, cognitive reappraisal skills, savoring of natural rewards and positive emotion regulation into an 8-week group therapy, is designed to target the attentional biases, affective dysregulation, and autonomic stress responses that underlie the feedback loop between chronic pain, craving, and opioid misuse ^{6,7} While MORE has shown positive outcomes in pain patients misusing, or at risk of misusing, opioids, it has not yet been tested in OUD patients with pain who are in recovery or receiving MAT. Therefore, we propose to test this promising intervention among individuals with pain who are receiving MMT for an OUD.

This study is significant because it could provide an additional and, as compared to existing behavioral interventions, a potentially more effective option for preventing relapse and managing chronic pain in people receiving MAT. Specifically, if found to be effective, MORE could help people on MAT cope with the stress and dysfunction associated with pain, reduce their risk of relapse, and enhance their overall quality of life.

1.3 Research Design and Methods

This study is a 2-arm individually randomized controlled trial design in which outcomes of MMT patients randomized to MORE, delivered remotely, by secure phone or video conferencing, are compared to outcomes of those randomized to treatment as usual (TAU). In the study we will randomize MMT patients with chronic pain to MORE or TAU. This study phase will conduct a clinical trial to assess MORE efficacy and to explore factors impacting the efficacy of MORE on opioid use outcomes. Participants with pain who are receiving MMT for an opioid use disorder (OUD) will be recruited from the New Brunswick Counseling Center (NBCC), Burlington Comprehensive Counseling, the Lennard Clinic, and Jersey Shore Addiction Services (JSAS).

A. Describe, in order of occurrence, all research procedures being performed, when and where they are performed, and by whom (including procedures being performed to monitor subjects for safety or minimize risks).

Participants will be recruited through flyers posted in the clinics, being approached by research assistants in the waiting room of their usual methadone clinic (New Brunswick Counseling Center, Burlington Comprehensive Counseling, Jersey Shore Addiction Services, or Lennard Clinic) if and when feasible, and referral by clinic staff. When a potential participant is referred by clinic staff, that means that the individual will be told about the study by staff and that it is up to the potential subject to volunteer by contacting the research staff on site or by phone. Alternatively, clinic staff will get permission from potentially eligible and interested individuals for the clinic to provide contact information to study staff for study staff to reach out to them for study recruitment by phone or in-person at their clinic or another safe and private location in the community (e.g., library, park, or coffee shop), if feasible. The number of individuals who contact the study staff through the flyers or referral and who are approached by study staff in the clinics will be tracked. Number of individuals who refuse study participation and who consent to the study will also be tracked. Patients expressing interest in the research will be given detailed study information by the RA and initial screening for study eligibility will be conducted over the phone or in-person at their clinic. Once a patient is screened as likely eligible, the RA will email or standard mail an informed consent form or an electronic link to access the consent form to the individual. Alternatively, the patient can pick up a copy of the consent at their respective clinic. Also, clinic staff will hand out consents to potentially eligible and interested individuals. Once the individual has a copy of the informed consent, the research assistant will review the informed consent and further assess eligibility over the phone or by secure, HIPAA compliant, video meeting or

4

Version Number: 15, 2/2/2022 Protocol Number: Pro20190016877 PI Name: [name]

Protocol Title: Mindfulness Oriented Recovery Enhancement (MORE) as an Adjunct to Methadone Treatment RESERVED FOR IRB STAMP
DO NOT MODIFY THIS SPACE

in-person. Participants will be asked to sign the electronic consent form on Qualtrics or REDCap, mail a signed paper version back to the research assistant, or drop off a signed paper version to their clinic for research staff to pick up. Alternatively, consenting maybe be done in-person. Participants will also keep a copy of the consent for their records.

Participants randomized to the MORE condition will participate in eight, weekly, two-hour online group sessions led by a clinic or study counselor. Each session will contain 5 to 9 participants and will be conducted online through secure video or phone conferencing. If a participant is unable to join the MORE session through video conference due to technical difficulties at the time of the session, the participant will be instructed to join the session by phone or the participant may go to their clinic and a research or clinic staff member can help them access the intervention through their tablet or a computer. Attendance at each session and reasons for missing sessions will be recorded. Participants randomized to the control condition will continue receiving treatment as usual at their clinic.

All study participants will partake in a total of three interviews lasting up to 120 minutes occurring at baseline, 8-, and 16-weeks (week 1 will be considered the week of the first MORE group session) by video or phone conferencing or in-person. If more than 3 months since baseline survey was administered from start of group (study intervention), clients will be asked to do another baseline survey. Each participant will also have a urine or saliva sample collected during each assessment. This is required to verify self-report of drug use. Due to social desirability, it is common for people to not accurately report drug use; therefore, biochemical verification is the gold standard measure of drug use. Participants will be mailed a urine or saliva test prior to the interview.

Alternatively, the patient can pick up urine or saliva test at their respective clinic. At the time of the interview, participants will be instructed on how to administer the test and will be instructed to show the research assistant the results on the video conference. The research assistant will then record the results. If a participant is unable or unwilling to attend a video meeting, a research assistant will conduct a telephone or in-person interview. If the interview is conducted by telephone, the participant will self-report their drug test results, and the fact that it was self-reported will be noted. Alternatively, when feasible, drug screen will be done in-person at their clinic. When drug tests cannot be completed, the reasons will be noted. Results from the most recent drug tests administered by the participants' clinics may also be obtained with participant consent.

All attempts to reach participants to schedule 8 and 16 week follow-up assessments will be tracked. If participant is not able to be reached by phone/email or in-person at clinic, follow-up letter for respective week will be mailed. Participants will also complete cognitive testing (for approx. 30-45 minutes) at baseline and 8-weeks and ecological momentary assessments (EMA) conducted during the entire study period via their own smartphone or computer, or tablet, which will be provided to each participant by study staff. Tablets from T-Mobile will be ordered on an as needed basis and based on t-mobiles availability. EMA participation will require the participant to respond to 3x-daily prompts in which they will be asked a series of brief questions regarding their current mood and exposure to opioid triggers. Additionally, subjects will be asked to initiate responses when they experience serious craving or relapse to opioid use. Each EMA assessment will last approximately 3-5 minutes. For those who do not complete their EMA, our research staff will do a timeline follow-back over the phone, video conferencing, or in-person to collect missing drug use data. Weekly EMA completion reports will be reviewed and a phone or in-person TLFB completed, as needed.

B. What data points will be collected including long-term follow-up?

All study participants will participate in three video, phone conferencing, or in-person visits at baseline, 8-, and 16-weeks. Information will be collected on demographic characteristics, substance use, methadone treatment, opioid craving and withdrawal, physical pain, non-reactivity, negative and positive affect, attentional bias, cognitive and

Version Number: 15, 2/2/2022 Protocol Number: Pro20190016877 PI Name: [name]

Protocol Title: Mindfulness Oriented Recovery Enhancement (MORE) as an Adjunct to Methadone Treatment RESERVED FOR IRB STAMP
DO NOT MODIFY THIS SPACE

mental health, physical health, and intervention implementation and attitudes. At the baseline and 8-week research visits, participants will complete three cognitive tasks on a computer or tablet that assess inhibitory control, implicit (automatic) associations, and the precedence of global features in visual perception. Urine and/or saliva samples will be requested at each assessment for confirmation of self-reported drug use or recent drug test results will be obtained from the participants' clinic chart. In addition, participants will partake in daily ecological momentary assessments (EMA) throughout the 16-weeks of study participation that include brief measures of pain intensity, mood, and substance use. Participants will also be asked to initiate communication via smartphone, computer, or tablet when they either lapse to opioid use or experience serious craving. Self-initiated responses will include information about the circumstances surrounding their craving/lapse. A synopsis of all study instruments are included below (see 1.98 – Study instruments).

C. Define the duration of the study and the length of time each subject will participate in the study. This study is expected to take two years. Each subject will participate in the study for a total of 16-weeks.

- **D.** Describe any primary and secondary study or safety endpoints
 - Primary Outcome: time until opioid relapse
 - Secondary Outcomes: opioid abstinence, days of drug use, MMT adherence, craving, pain symptoms, and emotional distress

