1.6 Study Variables

A. Independent Variables, Interventions, or Predictor Variables

Mindfulness Oriented Recovery Enhancement (MORE) structure (Intervention Condition). The MORE arm will participate in eight, weekly, two-hour group sessions led by a therapist on video or phone conference. MORE sessions involve mindfulness training to prevent opioid relapse and reduce pain, cognitive reappraisal to decrease negative affect and regulate opioid craving, and savoring to augment natural reward processing and evoke positive emotion. Each session begins with a mindful breathing or body scan meditation, followed by a debriefing session, in which the therapist provides reinforcement and troubleshooting to help guide successful implementation of mindfulness techniques. Following this debrief of the in-session mindfulness meditation, the therapist debriefs participants' homework practice of using mindfulness, reappraisal, and savoring skills to cope with pain and enhance well-being in everyday life. During this debrief of the homework practice, the therapist provides reinforcement and troubleshooting to help guide successful implementation of mindfulness, reappraisal, and savoring techniques. Next, new psychoeducational material is introduced according to the session topics outlined in Table 3. Sessions culminate with an experiential exercise, and close with a brief mindful breathing meditation. Participants are asked to practice 15 minutes of mindfulness/reappraisal/savoring skills each day (i.e. homework practice).

Table 3. MORE session content								
Week	Theme							
1	Introduction to mindfulness, and the relationship between nociception, pain and emotional suffering; mindful breathing and body scan							
2	Automatic pain coping habits; awareness of automatic opioid use; instruction in mindfulness of automatic pilot; mindful breathing							
3	Mindful reappraisal as means of coping with negative emotions; mindful breathing							
4	Savoring natural rewards; positive emotion regulation; mindful savoring practice							
5	Mindfulness of opioid craving; contemplation of negative consequences of opioid use; imaginal opioid cue-exposure; mindful breathing							
6	The relationship of the stress response to pain and craving; imaginal stress exposure; mindful breathing; body scan							
7	Concepts of thought suppression, aversion, and attachment; exercise in the futility of thought suppression; mindful breathing and acceptance							

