1.9 Interviews, Focus Groups, or Surveys

A. Administration

Timing and Frequency

Research staff will collect interview data and drug screens from both intervention and control group subjects through video, phone interview, or in-person using standardized measures conducted at baseline and 8- and 16-weeks. Cognitive testing data will be collected at baseline and 8-weeks. If the research assessments are conducted over the phone, drug screen results will be recorded as self-reported. Additionally, subjects will engage in twice-daily EMA assessments of approximately 3-5 minutes each for 16-weeks. For 16-weeks, subjects will also initiate EMA communications to report lapses or serious cravings, which will also last for under 5 minutes. For those who do not complete their EMA, our research staff will do a timeline follow-back over the phone or video conferencing to collect missing EMA drug use data. EMA completion reports will be reviewed, weekly, and participants will be contacted, as needed, to collect missing daily drug use data.

Location

The assessments and drug screens will take place via video/online, phone interview, at their clinic, or at another safe and private location in the community (e.g., library, park, or coffee shop).

Procedures for Audio and Visual Recording

Audio or video recordings will be made of the MORE therapy sessions. All recordings will be stored in password protected computers, in a locked office at [name], or in password protected files, on the Rutgers network or HIPAA compliant Box file.

9

B. Study Instruments

Version Number: 15, 2/2/2022 Protocol Number: Pro20190016877 PI Name: [name]

Protocol Title: Mindfulness Oriented Recovery Enhancement (MORE) as an Adjunct to Methadone Treatment RESERVED FOR IRB STAMP
DO NOT MODIFY THIS SPACE

- Time until first opioid lapse assessed through ecological momentary assessment data and timeline follow-back.
- Time until MMT dropout assessed through clinic records (abstracted by the study counselor who will have access to the clinic records). Time until dropout will be calculated from enrollment until last dose of methadone.
- Total days of methadone treatment assessed through clinic records (abstracted by the study counselor who will
 have access to the clinic records). Number of days will be calculated from enrollment until each follow-up timepoint.
- Total days of opioid or any drug use assessed through EMA data and timeline follow-back

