PI Name: [name]

Protocol Title: Mindfulness Oriented Recovery Enhancement (MORE) as an Adjunct to Methadone Treatment RESERVED FOR IRB STAMP DO NOT MODIFY THIS SPACE

Savoring (Baseline, 8- and 16-- weeks). Savoring will be measured by the Savoring Beliefs Inventory (SBI), The SBI is a reliable and valid scale that consists of 6 items that assess individuals' perceptions of their ability to derive pleasure through anticipating upcoming positive events, savoring positive moments, and reminiscing about past positive experiences or the Momentary Savoring Scale,²⁷ which assesses the propensity to focus on the moment as a means of intensifying positive experience from naturally rewarding events.

Mindfulness practice. In addition to collecting EMA data we will assess mindfulness practice with the timeline follow-back. The timeline follow-back is a reliable and valid measure where participants are asked to recall and record events within a specified time period on a calendar.

MMT dose, MMT days of treatment, MMT services. This information will be abstracted from participants' clinic charts, with participants' consent.

The following cognitive tasks will be completed on a laptop computer or tablet. The online tasks will be administered through the Inquisit platform. Pre-developed Inquisit scripts exist for each computer task, and participants' encrypted task data will be housed on a secure server "using Secure Sockets Layer (SSL)", the same technology used by online shopping and banking web sites to protect sensitive information transmitted over the web" (https://www.millisecond.com/support/docs/v5/Inquisit.pdf). Each task will be scored within the Inquisit platform according to validated scoring methods.

Inhibitory control, Go-No Go Task (Baseline, 8-weeks): To assess inhibitory control, participants are asked to press the Spacebar on a computer when they see, on the computer screen, a green rectangle (=go) but refrain from pressing the Spacebar when they see a blue rectangle (=no go).²¹ The blue and green rectangles can be vertical or horizontal. The vertical rectangle has a high probability of being green (a go trial) and the horizontal rectangle has a high probability of being blue (a nogo trial). Participants get information about the orientation of the rectangle (=cue) shortly before the color of the rectangle is revealed. Mean reaction times will be derived from the Go/No-Go tasks.

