Hypothesis 1.1. (**Primary Outcome**) MORE will result in longer duration of time to first opioid lapse and MMT dropout than TAU. We will use survival analysis (Kaplan Meier curves and marginal model analysis for multivariate survival data)³⁴ to test effects of MORE vs. TAU on time until first opioid lapse and MMT dropout—evidenced either on EMA, Timeline Follow-Back, urinalysis or medical records (whichever is first). Survival analysis will be run once, at 16 weeks post-baseline. Clustering within cohort will be adjusted in the multivariate marginal model analysis.³⁴ We will estimate the hazard ratios of opioid lapse and MMT dropout when comparing MORE with TAU, controlling for covariates.

Hypotheses 1.2 and 1.3 (Secondary Outcomes). MORE will result in more days of opioid abstinence (or less days of use) and a higher rate of biochemically-verified abstinence over time than TAU. Generalized linear mixed model (GLMM)³⁵ repeated measures analysis will be used. Specifically, identity link will be used for "number of abstinent days" as the dependent variable, and logit link will be used for "opioid abstinence (yes/no via urinalysis)" as the dependent variable. Days of use/abstinence will be assessed via EMA, number of drug use days since last visit and past 30 days, and the Timeline Follow-Back. In cases of conflicting findings across data sources, we will assume the highest number of days of use or lowest number of abstinent days recorded for that period. Analyses will include group (MORE vs. TAU), time, and group by time interactions as the fixed effects independent variables. Correlations among repeated measures and among subjects within cohorts will be modeled using nested random effects. Potential confounders that meet the p<0.10 criterion stated above will be entered as covariates. Linear contrasts will be constructed to test between-group differences in "days of use" or "days of abstinence" separately at each timepoint. In comparing days of use, if a substantial proportion of subjects do not use opioids, resulting in excessive zero days of use, we will use a two-part logistic/linear analysis model.^{36,37}

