All investigators and research staff will have undergone mandatory education in human research participant protection. To assure confidentiality, data will be secured in a database management system, password protected files, and in secure file cabinets. Data collection forms, databases, and recordings will not include identifiers other than a study ID code. The key to the code will be kept separately in a locked and/or password protected file for no longer than six years. Informed consent forms will be kept separately in a locked file in the same office. Three levels of security are provided to prevent unauthorized persons from accessing the data: password protection, computer or file cabinet locks, and a locked office. In addition, we have a Certificate of Confidentiality from the National Institutes of Health that protects study data from subpoena. Access to data will be limited study investigators and staff. Research data will be kept no longer than 10 years.

D. Describe any procedures that will be used for quality control of collected data.

As we have done in prior studies, protocols will be developed during the initial start-up period that explicitly describes the specific procedures related to data collection, entry, storage, and quality assurance for both study conditions. Data will be collected by research staff in strict accordance with the study's protocols. All data collected will be independently reviewed for quality and consistency by a member of the research team who was not responsible for collecting the source data. The research staff will be trained to avoid omissions in data collection and data entry. Computer entry protocols will be programmed to avoid accidental skipping of question items. We will apply conditional formatting to datasheets to remove the possibility of out of range data. Data will be entered directly into a secure Qualtircs or REDCap databases. Under supervision from [name], the Research Assistant will conduct monthly descriptive summaries on all data to ensure their accuracy. This will not involve completing any statistical comparisons. If problems are noted in data entry (e.g., out of range values, missing values), the Research Assistant and [name] will investigate the root cause, and solutions to rectify the problem will be generated and implemented.

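### The protocol allows, without requiring, the same counselor role to lead MORE groups and to abstract MMT dropout and MMT days, and it states neither separation of the two tasks nor masking of the abstractor

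*Combined protocol and SAP*

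**What the plan says.** **Who delivers MORE.** Section 1.3 A describes "eight, weekly, two-hour online group sessions led by a clinic or study counselor". Section 1.6 A uses a different term: "eight, weekly, two-hour group sessions led by a therapist on video or phone conference". Neither identifies the leader further.

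**Who reads the clinic records.** Section 1.9 B lists "Time until MMT dropout assessed through clinic records (abstracted by the study counselor who will have access to the clinic records", and makes the same attribution for total days of methadone treatment. The dating rule for dropout is "Time until dropout will be calculated from enrollment until last dose of methadone". A later entry in 1.9 B on MMT dose, days and services names no abstractor: "This information will be abstracted from participants' clinic charts, with participants' consent".

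**Where these outcomes are used.** Hypothesis 1.1 in section 6.1 A, labelled as the primary outcome, covers both first opioid lapse and MMT dropout. The endpoint list in 1.3 D gives opioid relapse alone as primary and puts MMT adherence among the secondary outcomes; 1.6 B marks only first opioid lapse as primary. Total MMT days is tested under Hypothesis 1.4, as secondary.

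**What check exists.** Section 6.1 D says all collected data are "independently reviewed for quality and consistency by a member of the research team who was not responsible for collecting the source data".

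**The concern.** A counselor who leads a MORE group knows which participants are in MORE. That counselor spends up to 16 hours with them (eight sessions of two hours) and is placed to learn why they miss sessions, which 1.3 A says will be recorded. Group leadership brings no matching contact with TAU participants. If the same person then opens the charts to decide when each participant stopped methadone, ambiguous records may be resolved differently in the two arms.

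The direction is not predictable. A wish to see the treatment succeed would favour MORE, while fuller knowledge of MORE participants' absences could count against it. Either way, a difference in ascertainment would look like a treatment effect and could not be separated from one afterwards. What is at stake is the dropout part of Hypothesis 1.1 and the secondary comparison of MMT days.

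**Working it through.** **1. The roles, side by side.**

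| Task | Role named | Place |
|---|---|---|
| Lead MORE groups | clinic or study counselor | 1.3 A |
| Lead MORE groups | therapist | 1.6 A |
| Abstract MMT dropout | study counselor | 1.9 B |
| Abstract total MMT days | study counselor | 1.9 B |
| Abstract MMT dose, days, services | none named | 1.9 B, later entry |
| Collect interviews and drug screens | research staff | 1.9 A |
| Timeline follow-back for missing EMA drug use | research staff | 1.3 A, 1.9 A |

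The study counselor is one of two permitted group leaders and the only abstractor named for dropout and MMT days. The overlap is permitted; it is not stated to occur.

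**2. Room for judgement.** The item is the date of the last methadone dose, taken from records the abstractor is not said to create. However, 1.9 B gives no length of gap that counts as dropout and no rule for interrupted dosing or transfers. Section 1.6 A describes take-home doses and says their timing, and the scheduling of clinic days, differ between clinics. The last attendance, the last dispensing and the last dose taken can therefore fall on different dates.

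**3. The existing check.** The review in 6.1 D is by a second person and concerns quality and consistency. It is not described as masked or as a second reading of the chart. A plausible date that was influenced by knowledge of the arm could pass it.

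**4. Illustration of sensitivity.** The plan gives no misreading rate and no expected number of dropouts, so there is no figure of its own to reproduce. Inputs: about 50% discontinuation within 12 months among people who begin MMT (1.2); 16 weeks = 112 days; 92 per arm (1.5). Assumptions: constant hazard, equal true hazards, all misreadings in the MORE arm and in one direction.

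- 16-week dropout: 1 − exp(−(ln 2 / 365) × 112) = 0.192
- Expected dropouts per arm: 92 × 0.192 ≈ 17.6 (unrounded proportion 0.1916)
- Apparent hazard ratio when k MORE dropouts are read as retained: ln(1 − (17.6 − k)/92) / ln(1 − 0.192)

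| k | Read as retained (17.6 − k) | Same number in error the other way (17.6 + k) |
|---|---|---|
| 1 | 0.94 | 1.06 |
| 2 | 0.88 | 1.13 |
| 3 | 0.81 | 1.19 |
| 4 | 0.75 | 1.26 |

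Four misreadings are 4/17.6 = 23% of the MORE dropouts, a large error rate for a dosing date.

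The 50% applies to people starting MMT, whereas the trial enrols anyone currently on methadone (4.2 D). If 12-month discontinuation were 25% instead (my assumption, to show a range), 16-week dropout would be 1 − exp(ln(0.75) × 112/365) = 0.084, or 7.8 of 92. One or two MORE dropouts read as retained would then give 0.87 or 0.73. Fewer events make each misreading weigh more, but also leave fewer dropouts to misread.

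**The case against.** **The overlap may never happen.** Section 1.3 A says clinic or study counselor. Where a clinic counselor leads, the study counselor may not meet the group at all. A reader might infer that the person who delivers MORE does read the outcome. The documents do not say that. Parts of the protocol, between 1.10 and 2.2 and just before 3.0, were not in the text available for this review and may deal with staff roles. This objection stands: the point is about what the plan permits.

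**Lapse data are not involved.** Hypothesis 1.1 accepts events "evidenced either on EMA, Timeline Follow-Back, urinalysis or medical records (whichever is first", and a reader might infer that the counselor also reads charts for lapses. No section gives the counselor that task. In 1.9 B first lapse comes from EMA and timeline follow-back, and research staff carry out the follow-back and the drug screens. The entry on clinic drug tests names no abstractor. This stands too.

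**Dropout is not the listed or powered primary endpoint.** Sections 1.3 D and 1.6 B name only relapse or lapse as primary, and the power analysis in 6.1 B uses relapse. That is correct and lowers the stakes. It does not remove them, because Hypothesis 1.1 still tests dropout under the primary label.

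**A last-dose date is fairly objective, and a second person reviews the data.** Largely so. The remaining judgement comes from a missing definition that would affect any abstractor. But an abstractor who leads groups brings extra knowledge about one arm only, and the review is not described as masked.

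**Masking is hard here.** Section 1.3 A lets research staff help participants get into MORE sessions, and the EMA described in 1.9 B asks the intervention group about homework. Full masking of the existing assistants cannot be assumed. This limits the fix, not the point.

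**Conclusion.** The point holds in a limited form. The plan permits one role both to deliver MORE and to abstract MMT dropout and MMT days, and the text available neither separates the tasks nor masks the abstractor. The conclusion is confined to those two outcomes. It does not reach the listed primary endpoint of opioid relapse or lapse, and it does not show that the same individual will do both tasks or that bias will occur.

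The size cannot be estimated from the documents. The hazard ratios of 0.94 to 0.75 are only an illustration. They assume 50% 12-month discontinuation among people who begin MMT, a constant hazard, no true effect, and misreadings confined to MORE and all in one direction; the reverse direction is equally open. They show that a few dates could matter when events are few. This is an inexpensive improvement worth making, not a flaw that undermines the trial.

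**What to change.** In section 1.9 B, replace the assignment to the study counselor with a statement that:

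- MMT dropout and total MMT days are abstracted by a study team member who leads no MORE group;
- one fixed form, or an extract of the clinic dosing record, is used identically in both arms;
- the arm is withheld from the abstractor where feasible;
- MORE group leaders do not abstract or adjudicate outcomes.

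The form should also record how last attendance, last dispensing and last dose are told apart, since 1.9 B leaves this open. The later 1.9 B entry on MMT dose, days and services should name the same abstractor.

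The cost is protocol wording, reassignment of one task, and arranging chart access or extracts for that person. Section 4.6 B already has participants sign a release for the clinic to give information to the study team. Separation is easy to achieve with existing staff. Masking is harder, so it should be stated as an aim rather than a guarantee.
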